7.4.1.3 Assessment of Health

Days 10 to 14

The patient will self-assess his or her health on a scale of 0 (Worst possible health) to 10 (Normal health [for someone your age and condition]) and record it in the patient eDiary, predose on Day 1 and then once daily (evening) until Day 14. Table 7-3 provides the time windows of assessment as a guide.

Time Windows of Assessment as a Guide: Assessment Table 7-3 of Health

Assessment Period	Time Period of a Day	Time Window as a Guide
Days 1 to 14	Evening	18:00 -

Assessment of health prior to influenza symptoms will be performed predose on Day 1 and recorded in either the eDiary or a paper diary (see Appendix 4).

CPI 7.4.1.4

TheCPI will be recorded in the patient eDiary. The details of the measurement are described in the Section 7.7.4.1.

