7.9.3 Other Endpoints

The benefits of S-033188 in improving QOL can be examined by assessing the time to return to preinfluenza health status and the change in the score of the QOL questionnaire CPI

An understanding of potential amino-acid substitutions in S-033188-exposed patients will be gained by exploring polymorphic and treatment-emergent amino acid substitutions in

the PA gene in S-033188-exposed patients at baseline and at the last evaluable time point, with sequencing of approximately 100 placebo-exposed patients performed as a control.

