8) Time to improvement in the 3 respiratory symptoms (cough, nasal congestion, and sore throat)

Defined as the time between the initiation of the study treatment and the improvement in the 3 respiratory symptoms. The assessment follows the criteria for the primary endpoint.

9) Time to resolution of fever

Defined as the time between the initiation of the study treatment and the resolution of fever. The resolution of fever is defined as the time when the patient's self-measured temperature becomes $< 37^{\circ}$ C and is maintained at $< 37^{\circ}$ C for a duration of at least 12 hours.

10) Proportion of patients reporting normal temperature at each time point

Defined as the percentage of patients whose temperature resolves to $< 37^{\circ}$ C after the initiation of the study treatment in the analysis population.

11) Body temperature at each time point

Defined as measured axillary temperature.

12) Time to improvement of each influenza symptom

Defined as the time between the initiation of the study treatment and the alleviation of each influenza symptom. The alleviation of a symptom is defined as the time when the symptom is assessed as 0 (None) or 1 (Mild), for a duration of at least 21.5 hours (24 hours -10%).

13) Time to return to preinfluenza health status

Patients will be asked to record their preinfluenza health status between 0 (worst possible health) and 10 (normal health [for someone your age and your health condition]). Return to preinfluenza health status is defined as time from the initiation of the study treatment to time to the same number on scale for preinfluenza health status.

14) Requirement for systemic antibiotics for infections secondary to influenza infection

Defined as the percentage of patients treated with systemic antibiotics.

15) Incidence of influenza-related complications (hospitalization, death, sinusitis, bronchitis, otitis media, and radiologically confirmed pneumonia)

Defined as the percentage of patients in the analysis population who experience each influenza-related complication (hospitalization, death, sinusitis, otitis media, bronchitis, and radiologically-confirmed pneumonia) as an adverse event after the initiation of the study treatment. A specific complication eCRF with diagnostic criteria for the complications of sinusitis, otitis media, bronchitis, and pneumonia will be provided.

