8) Time to improvement in the 3 respiratory symptoms (cough, nasal congestion, and sore throat)

The same analyses as the primary endpoint will be performed.

9) Time to resolution of fever

The same analyses as the primary endpoint will be performed.

10) Proportion of patients reporting normal temperature at each time point

The summary table by each time point will be made. The Mantel-Haenszel test at each time point will be used to compare the proportion of resolution of fever between S-033188 and oseltamivir/placebo with baseline symptom score (≤ 14 , ≥ 15), preexisting and worsened symptom (Yes, No), and region (Asia, North America/Europe, Southern Hemisphere) as stratification factors.

11) Body temperature at each time point

The summary table by each time point will be made. The analysis of covariance (ANCOVA) will be used by each time point to compare body temperature between S-033188 and oseltamivir/placebo, where composite symptoms score at baseline, and preexisting and worsened symptom (Yes, No), and region (Asia, North America/Europe, Southern Hemisphere) will be used as covariates.

12) Time to improvement of each influenza symptom

The same analyses as the primary endpoint will be done. Patients whose symptoms at baseline are assessed as 0 (None), 1 (Mild), 2 (Moderate) but preexisting and not worsened, or 3 (severe) but preexisting and not worsened will be excluded from the analysis.

13) Time to return to preinfluenza health status

The same analyses as the primary endpoint will be performed.

14) Requirement for systemic antibiotics for infections secondary to influenza infection

A summary table will be created. The Fisher's exact test will be used to compare the percentage of patients who used systemic antibiotics for infections secondary to influenza infection between S-033188 and oseltamivir/placebo.

15) Incidence of influenza-related complications (hospitalization, death, sinusitis, bronchitis, otitis media, and radiologically-confirmed pneumonia)

A summary table will be created. Fisher's exact test will be used to compare the incidence between S-033188 and oseltamivir/placebo.

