Appendix 4 Assessment of Health Scale

Health scale

Pre-flu health:

Please circle on the line below one number between 0 (worst possible health) and 10 (normal health for someone your age and your health condition) which best describes your pre-flu health.

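### Return to preinfluenza health is counted only on an exact match of the 0–10 score, so a patient who passes that score is counted late or not at all

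*Protocol*

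**What the plan says.** All of the following is in the protocol.

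- **Event.** Section 9.10.2, item 13, defines the endpoint as "time from the initiation of the study treatment to time to the same number on scale for preinfluenza health status".
- **Target score.** The same item says "Patients will be asked to record their preinfluenza health status between 0 (worst possible health) and 10". Appendix 4 has the patient circle one number, with the top of the scale labelled "10 (normal health for someone your age and your health condition) which best describes your pre-flu health". Section 7.4.1.3 fixes the timing: "Assessment of health prior to influenza symptoms will be performed predose on Day 1". It is a single recalled value, and values below 10 are allowed.
- **Follow-up score.** Section 7.4.1.3 has current health rated on the same 0–10 range, "predose on Day 1 and then once daily (evening) until Day 14". That gives at most 14 postdose readings.
- **Analysis.** For item 13, Section 9.10.3.2 says "The same analyses as the primary endpoint will be performed", meaning the stratified generalized Wilcoxon test and Kaplan-Meier summaries.
- **Use.** Section 7.9.3 says that quality-of-life benefit "can be examined by assessing the time to return to preinfluenza health status", alongside a questionnaire.

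None of these places says that a score above the preinfluenza number also counts.

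**The concern.** The rule is an equality on a scale that is read only once a day. A patient whose preinfluenza score is below 10 can be under it one evening and over it the next. By the endpoint's own name that patient has returned to preinfluenza health, yet no event is recorded. An event comes later only if reported health falls back to the exact number, so a decline would then be dated as the recovery. If the score does not fall back by Day 14, the patient has no event.

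The neighbouring endpoints do not behave this way. Alleviation of a symptom accepts either of the two lowest grades, and resolution of fever accepts any temperature under 37°C. Item 13 alone asks for a single value.

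The error is not neutral between groups. Larger daily gains make it more likely that the number is stepped over, so the group that recovers faster tends to lose more time to the rule. A real difference between S-033188 and placebo or oseltamivir would tend to look smaller on this endpoint.

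**Working it through.** The protocol gives no power, event count or effect size for this endpoint, so there is no figure to reproduce. The check compares two rules on the same diaries. Let P be the preinfluenza score and Y(d) the evening score on day d:

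- as written: T= is the first d with Y(d) = P
- threshold: T≥ is the first d with Y(d) ≥ P

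**Hand-built diaries**

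| P | Evening scores | T= | T≥ |
|---|---|---|---|
| 8 | 3, 4, 6, 7, 9, then 10 to Day 14 | no event | Day 5 |
| 8 | 3, 4, 6, 7, 9, 9, 9, 8, then 9 to Day 14 | Day 8 | Day 5 |
| 10 | 3, 4, 6, 7, 9, then 10 to Day 14 | Day 6 | Day 6 |

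No score can exceed 10, so at P = 10 the two rules always agree. Below 10 they can differ.

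**Illustrative simulation (every input is an assumption)**

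- 200,000 patients per setting and 14 evening readings; P = 7 and Day 1 score 3.
- Latent score L(d) = min(3 + sum of daily gains, 7 + k). Gains are gamma with shape 2 and mean 0.8 (slow), 1.2 or 1.8 (fast) points per day.
- Y(d) = L(d) plus normal noise with SD 0.5, rounded and held within 0–10.
- k = 0, 0.5 or 1 is how far above P the patient settles.
- Never counted: T≥ occurs by Day 14 but T= does not. Late: T= falls after T≥. Means are restricted to 14 days.

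| Settling level | Never counted | Late | Mean delay (days) | Slow − fast, as written | Slow − fast, threshold |
|---|---|---|---|---|---|
| (a) at P | 0% | 12–16% | 0.2 | 2.23 | 2.28 |
| (b) P + 0.5 | about 0.1% or fewer | 22–35% | 0.5 (slow) to 0.7 (fast) | 2.04 | 2.32 |
| (c) P + 1 | 6–7% | 22–43% | 1.2 to 2.7 | 0.87 | 2.33 |

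Relative loss of the difference in means:

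- (a) (2.28 − 2.23)/2.28 = 2%
- (b) (2.32 − 2.04)/2.32 = 12%
- (c) (2.33 − 0.87)/2.33 = 63%

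The settling level matters so much because a settled patient who has skipped 7 must wait for noise to bring the score back. The chance of reading 7 on a given evening is:

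- settled at 7: Φ(1) − Φ(−1) = 0.68
- settled at 7.5: Φ(0) − Φ(−2) = 0.48
- settled at 8: Φ(−1) − Φ(−3) = 0.16

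**Mixture, half with P = 10 and half with P = 7.** Slow minus fast, as written against threshold, is 3.29 against 3.31 in (a), 3.20 against 3.34 in (b) and 2.61 against 3.34 in (c). The losses are about 1%, 4% and 22%.

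**A second model** used exponential recovery from 3 at 0.15–0.5 per day, noise SD 0.5–1.0, a plateau around P + 0.5 that varied between patients, and P from 6 to 9. Among patients who reached or passed P, about 3–29% were counted late and 0.2–6% never. At P = 10 both were 0%.

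The order of the groups did not reverse in any setting of the first simulation. The second had no group comparison.

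**The case against.** Several points stand against giving this much weight.

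- **The wording may only be loose.** The endpoint is called a return to preinfluenza health, and a patient at 8 with a preinfluenza 7 has plainly returned. A SAP not shown here may read it that way. But Section 9.1 has the SAP follow the protocol and explain departures, and the protocol states the event itself. A SAP that kept to the text would carry the problem forward.
- **The scale limits exposure.** Because 10 is anchored to the patient's own age and condition, a stable high-risk patient can properly answer 10. The share below 10 is not given and may be small. This stands.
- **Large effects need patients to settle above their recalled preinfluenza level within 14 days.** The protocol gives no evidence for that. If they settle at it, the loss is small. This stands.
- **Restricted means are not the planned summary.** The protocol plans medians. In (a) and (b) these are 5 days (slow) and 3 days (fast) under both rules; only in (c) does their difference change, 1 day against 2. Medians on a daily grid are coarse, and at an intermediate rate in (b), 1.37 points per day, the median did move from 3 to 4 days.
- **The simulated contrast is wide.** It is 1.8/0.8 = 2.25-fold, whereas the sample-size assumption for the primary endpoint is 150/114 = 1.32-fold. At 0.8 against 1.05 points per day, the mean differences are 0.95 against 0.97 in (a), 0.88 against 0.98 in (b) and 0.50 against 0.99 in (c). The absolute losses are smaller, but in (c) about half the difference still goes.
- **The bias does not favour S-033188 if S-033188 works faster.** It tends to hide a benefit. That lowers the stakes but does not make the rule right.

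These points limit the likely size. None shows that the rule gives the right event for a patient who passes the preinfluenza score.

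**Conclusion.** The concern holds. Item 13, followed as written, gives the wrong event time, or none, for a patient with a preinfluenza score below 10 who steps over it. This follows from the text and the once-daily schedule and needs no assumption.

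How much it matters in this trial is unknown. The protocol gives neither the share of patients below 10 nor how far patients settle above their recalled score. The illustrations run from negligible (everyone scores 10, or patients settle at their preinfluenza level) to more than half the mean difference lost (every patient has a preinfluenza score of 7 and settles a full point above it).

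The consequence is confined to one secondary endpoint outside the stated testing hierarchy. The primary analysis and the sample size are untouched. The correction should be made because the rule is plainly not what the endpoint's name intends, and because choosing between two readings after unblinding would be hard to defend.

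**What to change.** In Section 9.10.2, item 13, define the event as the first postdose evening score equal to or higher than the patient's preinfluenza score. Use the same definition in the SAP, fixed before unblinding.

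Leave the analysis set and the methods in Section 9.10.3.2 as planned. Item 13 sets no minimum duration at present, and this change adds none.

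The cost is one comparison in one sentence. No new data, visit or questionnaire is needed.

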9.10.3 Analyses of Efficacy Endpoints

9.10.3.1 Analyses of Primary Endpoint

9.10.3.1.1 Primary Analysis

The stratified generalized Wilcoxon test will be applied to the primary endpoint with some stratification factors, namely baseline symptom score ($\leq 14, \geq 15$), preexisting and worsened symptom (Yes, No), and region (Asia, North America/Europe, Southern Hemisphere) to evaluate the efficacy of S-033188 compared with placebo.

The same analysis in the PPS will be performed as a sensitivity analysis.

9.10.3.1.2 Secondary Analysis

The same analysis method and endpoint as the primary analysis will be used to evaluate the efficacy of S-033188 compared with oseltamivir.

Together with the primary efficacy analysis, this comparison will be conducted in a hierarchical manner so as to maintain control of overall type I error. For Japan, control of overall type I error is not required for the secondary efficacy analysis of primary endpoint.

The same analysis in the PPS will be performed as a sensitivity analysis.

9.10.3.1.3 Other Analyses

In addition, a Kaplan-Meier survival curve will be plotted for each group, and the median times, the differences of the median times, and their 95% CIs will be calculated.

The same analysis in PPS will be performed as a sensitivity analysis.

9.10.3.2 Analyses of Secondary Endpoints

1) Proportion of patients positive for influenza virus titer and proportion of patients positive by RT-PCR at each time point

Only patients whose virus titer/RT-PCR predose at Visit 1 are \geq the lower limit of quantification will be included in the analyses. The summary table by each time

point will be made. The Mantel-Haenszel test at each time point will be used to compare the proportion of patients with positive virus titer/RT-PCR between S-033188 and oseltamivir/placebo with baseline symptom score ($\leq 14, \geq 15$), preexisting and worsened symptom (Yes, No), and region (Asia, North America/Europe, Southern Hemisphere) as stratification factors.

2) Change from baseline in virus titer and the amount of virus RNA (RT-PCR) at each time point

Only patients whose virus titer/RT-PCR predose at Visit 1 are \geq the lower limit of quantification will be included in the analyses. The van Elteren test will be used by each time point to compare the S-033188 with oseltamivir/placebo, where baseline symptom score ($\leq 14, \geq 15$), preexisting and worsened symptom (Yes, No), region (Asia, North America/Europe, Southern Hemisphere) will be included as stratification factors. Summary statistics will be calculated by time point and by treatment group.

3) AUC adjusted by baseline in virus titer and in the amount of virus RNA (RT-PCR)

Only patients whose virus titer/RT-PCR predose at Visit 1 are \geq the lower limit of quantification will be included in the analyses. The same statistical methods as 2) change from baseline in virus titer and the amount of virus RNA (RT-PCR) at each time point will be used. Summary statistics will be calculated by treatment group.

4) Time to cessation of viral shedding by virus titer and by RT-PCR

Only patients whose virus titer/RT-PCR predose at Visit 1 are \geq the lower limit of quantification will be included in the analyses. The same analyses as the primary endpoint will be performed.

5) Proportion of patients whose symptoms has been alleviated at each time point

The same analyses as 1) proportion of patients positive for influenza virus titer and proportion of patients positive by RT-PCR will be used.

6) Time to alleviation of symptoms

The same analyses as the primary endpoint will be performed.

 Time to improvement in the 4 systemic symptoms (headache, feverishness or chills, muscle/joint pain, and fatigue)

The same analyses as the primary endpoint will be performed.

8) Time to improvement in the 3 respiratory symptoms (cough, nasal congestion, and sore throat)

The same analyses as the primary endpoint will be performed.

9) Time to resolution of fever

The same analyses as the primary endpoint will be performed.

10) Proportion of patients reporting normal temperature at each time point

The summary table by each time point will be made. The Mantel-Haenszel test at each time point will be used to compare the proportion of resolution of fever between S-033188 and oseltamivir/placebo with baseline symptom score (≤ 14 , ≥ 15), preexisting and worsened symptom (Yes, No), and region (Asia, North America/Europe, Southern Hemisphere) as stratification factors.

11) Body temperature at each time point

The summary table by each time point will be made. The analysis of covariance (ANCOVA) will be used by each time point to compare body temperature between S-033188 and oseltamivir/placebo, where composite symptoms score at baseline, and preexisting and worsened symptom (Yes, No), and region (Asia, North America/Europe, Southern Hemisphere) will be used as covariates.

12) Time to improvement of each influenza symptom

The same analyses as the primary endpoint will be done. Patients whose symptoms at baseline are assessed as 0 (None), 1 (Mild), 2 (Moderate) but preexisting and not worsened, or 3 (severe) but preexisting and not worsened will be excluded from the analysis.

13) Time to return to preinfluenza health status

The same analyses as the primary endpoint will be performed.

14) Requirement for systemic antibiotics for infections secondary to influenza infection

A summary table will be created. The Fisher's exact test will be used to compare the percentage of patients who used systemic antibiotics for infections secondary to influenza infection between S-033188 and oseltamivir/placebo.

15) Incidence of influenza-related complications (hospitalization, death, sinusitis, bronchitis, otitis media, and radiologically-confirmed pneumonia)

A summary table will be created. Fisher's exact test will be used to compare the incidence between S-033188 and oseltamivir/placebo.

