7.4.2 Virology Test

Two nasopharyngeal/pharyngeal swabs (nasopharyngeal swabs are the preferred method of virology collection as they are the most accurate, but pharyngeal swabs will be acceptable if nasopharyngeal swabs cannot be performed) will be collected predose at Visit 1 (Day 1 at the same time as the RIDT), Visit 2 (Day 2), Visit 3 (Day 3), Optional Visit 1 (Day 4), Visit 4 (Day 5), Optional Visit 2 (Day 6), and Visit 5 (Day 9), as well as at Visit 6 (Day 15) and Visit 7 (Day 22) if the investigator determines that flu symptoms are persisting. Specimens will be handled according to Section 7.6.4.5.

The virology testing facility (see Section 10.1) will perform virus typing and subtyping, determination of virus titer and viral RNA load, according to procedures or a protocol specified in a separate document. Access to the virological endpoints will be limited. Specific details of who will have access to each endpoint will be specified in a separate document.

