9.10.2 Secondary Efficacy Endpoints

The secondary efficacy endpoints include the following variables.

1) Proportion of patients positive for virus titer and proportion of patients positive by RT-PCR at each time point

Defined as the percentage of patients whose virus titer is not < the lower limit of quantification among those assessed for virus titer, and the percentage of patients with detectable virus RNA among assessed by RT-PCR, respectively.

2) Change from baseline in virus titer and in the amount of virus (RT-PCR) at each time point

Defined as the change from baseline in virus titer and the change from baseline in the amount of virus RNA, respectively. Baseline is defined as the last value obtained before the initial dose.

3) AUC adjusted by baseline in virus titer and in the amount of virus RNA (RT-PCR)

Defined as AUC, where AUC is the area under the curve, of change from baseline in virus titer and AUC of change from baseline in the amount of virus RNA, respectively. AUC is calculated using the trapezoidal method.

4) Time to cessation of viral shedding by virus titer and by RT-PCR

Defined as the time between the initiation of the study treatment and first time when the virus titer is < the lower limit of quantification and the time between the initiation of the study treatment and first time when virus RNA by RT-PCR is < the lower limit of quantification, respectively.

5) Proportion of patients whose symptoms has been alleviated at each time point

Defined as the percentage of patients whose primary endpoints are improved after the initiation of the study treatment in the analysis population by each time point. 6) Time to alleviation of symptoms (cough, sore throat, headache, nasal congestion, feverishness or chills, muscle or joint pain, and fatigue)

Defined as the time between the initiation of the study treatment and the alleviation of influenza symptoms. The alleviation of influenza symptoms is defined as the time when all of 7 influenza symptoms have been assessed by the patient as 0 (None) or 1 (Mild) in the patient eDiary, for a duration of at least 21.5 hours (24 hours -10%).

7) Time to improvement in the 4 systemic symptoms (headache, feverishness or chills, muscle/joint pain, and fatigue)

Defined as the time between the initiation of the study treatment and the improvement in the 4 systemic symptoms. The assessment follows the criteria for the primary endpoint.

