c The patient will measure or assess and record in the patient diary, body temperature 4 times daily (morning, noon, evening, and bedtime) from Days 1 to 3 and twice daily (morning and evening) from Days 4 to 14; assessment of health once daily (evening) from Days 1 to 14; the severity of influenza symptoms twice daily (morning and evening) from Days 1 to 9 and once daily (evening) from Days 10 to 14; and the CPI twice daily (morning and evening) from Days 1 to 9 and once daily (evening) from Days 2 or ET.

d Predose; if the study treatment is initiated at 18:00 or later on Day 1, the patient will not need to perform the Day 1 evening assessments.

e Including measurement of body weight.

f Height and body mass index will be measured at the predose examinations only.

g Urine pregnancy test will be performed only for females who are not diagnosed as postmenopausal.

h Predose.

i To be collected if the investigator determines that flu symptoms are persisting.

j If the investigator determines that flu symptoms are persisting at ET.

k Blood samples will be collected for the measurement of plasma drug concentrations once each at Visits 2 (Day 2) and 4 (Day 5). If circumstances permit, samples also will be collected within the period from 0.5 to 4 hours after the initial dose at Visit 1 (Day 1), at Visit 3 (Day 3), and at Visit 6 (Day 15).

Quality-of-Life Questionnaire Appendix 2

CPI

Study center name	
Patient identification code	
Visit	
Date	

Under each heading, please tick the ONE box that best describes your health TODAY.

CPI

CPI

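### At Day 15 and Day 22 the by-visit virology tests compare arms only among patients swabbed for persisting symptoms, a group selected by an outcome the drug is meant to change

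*Protocol*

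**What the plan says.** **Sampling.** Protocol Section 7.4.2 lists swabs from Day 1 to Day 9 without a symptom condition; those at Days 4 and 6 belong to optional visits. It then adds swabs at "Visit 6 (Day 15) and Visit 7 (Day 22) if the investigator determines that flu symptoms are persisting". Footnote i of the schedule in Appendix 1 repeats the rule: "To be collected if the investigator determines that flu symptoms are persisting".

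**Denominator.** Section 9.10.2 item 1) defines titer positivity as the "percentage of patients whose virus titer is not < the lower limit of quantification among those assessed for virus titer", and RT-PCR positivity as "the percentage of patients with detectable virus RNA among assessed by RT-PCR". A patient without a swab leaves the denominator and is not counted as negative.

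**Tests.** In Section 9.10.3.2 item 1), "The Mantel-Haenszel test at each time point will be used to compare the proportion of patients with positive virus titer/RT-PCR between" S-033188 and each comparator. In item 2), "The van Elteren test will be used by each time point to compare the S-033188 with oseltamivir/placebo". The only restriction on either item is measurable virus before dosing (at or above the lower limit of quantification). Neither item excludes Day 15 or Day 22.

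**Missing data.** Section 9.4 leaves missing values unreplaced in the primary analyses and mentions a predefined rule for a sensitivity analysis. It does not say how patients who were not swabbed count in the virology endpoints.

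**The concern.** Read together, these provisions mean that the Day 15 and Day 22 tests ask whether the arms have equal positivity, or equal change from baseline, among patients who are still ill. The secondary objective in Section 2.2 asks about efficacy against placebo and oseltamivir in patients with influenza, and Section 9.10.3.2 narrows that only to patients with measurable baseline virus.

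Persistence of symptoms arises after randomization, and the primary endpoint is built to show that the drug changes it. The sample size section plans on exactly that difference. Patients swabbed late in the S-033188 arm are therefore a smaller and probably differently selected group than those swabbed late in the placebo arm. A difference between the two groups, or the lack of one, cannot be read as a treatment effect on virus. At stake is how the late rows of two secondary virology tables are interpreted.

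**Working it through.** **1. The planning inputs.** Section 9.2 assumes exponential times, medians of 150 h (placebo) and 114 h (S-033188), follow-up of 336 h, 395 infected patients per arm and a two-sided 5% generalized Wilcoxon test with at least 90% power. Recalculation gives 90.5% (91.5% by simulation), and Table 9-1 reproduces within 2 points. These inputs are sound to reuse. The protocol gives no figure for the Day 15 or Day 22 virology tests.

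**2. Who would be swabbed.** Proxy: not yet improved on the primary endpoint. Share remaining at time t is s = 0.5^(t / median).

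| | Placebo (150 h) | S-033188 (114 h) |
|---|---|---|
| Day 15, 336 h | 0.5^2.24 = 21.2%; 395 × 0.212 = 84 | 0.5^2.947 = 13.0%; 395 × 0.130 = 51 |
| Day 22, 504 h | 0.5^3.36 = 9.7%; 38 patients | 0.5^4.421 = 4.7%; 18 patients |

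These counts are upper figures, because the baseline-virus restriction would reduce them. Day 22 extrapolates the planning curve beyond 336 h.

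**3. What equal true positivity looks like among the swabbed.** Let p be true positivity in all patients, s the share still symptomatic, a the share both positive and symptomatic, and OR the odds ratio between virus and symptoms. Then

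OR = a(1 − s − p + a) / [(p − a)(s − a)], and the reported proportion is a / s.

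The documents give neither p nor OR, so both are assumed. For p = 10% in both arms at Day 15:

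| OR | Placebo a / s | S-033188 a / s | Two-sided rejection |
|---|---|---|---|
| 1 | 10% | 10% | about 5% |
| 5 | 0.0519 / 0.2117 = 24.5% | 0.0366 / 0.1296 = 28.2% | about 8% |
| 10 | 0.0659 / 0.2117 = 31% | 0.0494 / 0.1296 = 38% | about 14% |

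Rejection rates are simulated with a single-stratum Mantel-Haenszel test. At OR 5 and 10 nearly all rejections go against S-033188. Over p of 5%, 10% and 20% and OR of 1 to 10, rejection is 4% to 14% at Day 15 and about 3% to 8% at Day 22.

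**4. Does selection explain the low power?** Take true positivity of 20% vs 10% at Day 15. Power among the swabbed is about 33% at OR 1, where there is no selection bias, and about 42% to 46% at OR 3 to 10. The same test with results on every patient would have 98%. Power is lowest where selection does no harm, so the shortfall comes mainly from having 84 + 51 = 135 swabs rather than 2 × 395 = 790.

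Item 2) needs a swab at the visit to compute a change, so it rests on the same subset. No separate simulation was made for the van Elteren test.

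**The case against.** The strongest reply is that the protocol discloses its denominator, does not list which visits count as time points, and leaves detailed methods to the statistical analysis plan, which is not at hand and may drop these visits. That plan could indeed narrow the tests. But the protocol itself fixes the sampling rule, the denominator, the tests and their application at every time point, and the combination is what fails. Disclosing the denominator does not make the arms comparable within it.

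The second reply concerns size, and most of it stands. No positivity rate or odds ratio is documented; diary non-improvement only approximates investigator judgment; and error above 10% needs an odds ratio near 10 within the range tried.

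A reader might draw four stronger conclusions that the documents do not support:

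- That selection hides a real antiviral benefit, citing 33% to 46% power against 98%. The loss is mainly one of swab numbers, and in these scenarios the direction stays correct.
- That the late percentages necessarily overstate residual virus. This needs a positive association between virus and symptoms.
- That the distortion is severe. If no unswabbed patient carries virus, 4% in both arms becomes 4 / 21.2 = 18.9% vs 4 / 13.0 = 30.9% at Day 15, with about 36% rejection. That is a limiting assumption, and nothing in the protocol establishes it.
- That these rows are the trial's evidence on late shedding. Section 7.9.2 assigns viral shedding to time to cessation, a separate endpoint.

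**Conclusion.** The concern holds in a limited form. As written, items 1) and 2) test the arms at Days 15 and 22 within a subset selected by a treatment-affected outcome, and so do not answer the stated question for patients with measurable baseline virus. That conclusion is structural and needs no assumed rates.

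The size does rest on assumptions. Under the planning medians the swabbed groups are small and unequal, and under a positive virus-symptom association the bias runs against the faster-recovering arm. The resulting inflation of error at Day 15 ranges from none to moderate, and at Day 22 it is slight over odds ratios of 1 to 10.

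The problem touches two late visits of two secondary endpoints outside the stated hierarchy. The primary analysis and the virology results through Day 9 are not affected. It should be corrected, but it does not threaten the trial's main conclusion.

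**What to change.** In Section 9.10.3.2 items 1) and 2), limit between-group tests and summary percentages to visits whose swabs carry no symptom condition, that is, through Day 9: the scheduled Days 2, 3, 5 and 9, with the optional Day 4 and Day 6 visits left as now planned.

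For Days 15 and 22, make no between-group test. Report per arm the number swabbed and the number positive, show the full analysis set as the base, and label the results as symptom-triggered samples. Carry the same wording into the statistical analysis plan.

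The change is one of wording and needs no extra samples. It costs the p-values at Days 15 and 22 for these two secondary endpoints. It does not recover power at those visits, because patients who were not swabbed have no result to analyze.
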